- Hematology assessment includes: RBC count, Hb, hematocrit (Hct), mean corpuscular volume (MCV), mean corpuscular hemoglobin (MCH), mean corpuscular hemoglobin concentration (MCHC), red blood cell distribution width (RDW), white blood cell (WBC) count (corrected by erythroblast count) and differential count, absolute neutrophil count (ANC), and absolute lymphocytes count, platelets, (all previously listed assessments by central and local laboratory) absolute reticulocyte, and circulating erythroblasts (nucleated RBC) counts (by local laboratory) – 2 Hb measurements are required, by central laboratory at ≥ 1 -week intervals at Week -4 and at Week -3 or Week -2.
- Serum chemistry panel 1 (calcium, magnesium, phosphorus, blood urea nitrogen [BUN], creatinine, creatinine clearance, microalbumin, total protein, alkaline phosphatase, bilirubin [total, non conjugated], aspartate aminotransferase/serum glutamic oxaloacetic transaminase [AST/SGOT], alanine aminotransferase/serum glutamic pyruvic transaminase [ALT/SGPT], lactic dehydrogenase [LDH], and uric acid) - central laboratory assessment should be performed within 4 weeks prior to Dose 1 Day 1 (Local laboratory results are accepted at screening only if central laboratory results are not available in timely manner to allow eligibility assessment).
- Urinalysis: microalbumin, creatinine, microalbumin/creatinine ratio (morning void) - central laboratory assessment should be performed within 4 weeks prior to Dose 1 Day 1). Local laboratory results at Screening are accepted only if central laboratory results are not available in timely manner to allow eligibility assessment.
- MRI for LIC (mg/g dw) by T2* or R2, as per site's practice (to be performed during Screening, only if subject has not had MRI performed within 12 weeks prior to signing ICF)
- MRI for extramedullary masses - only for subjects who have history of masses at baseline
- MRI of spleen, if not splenectomized - MRI is the preferred technique (same MRI acquisition of LIC, if possible), the longest longitudinal dimension and width should be used. Alternatively, ultrasound can be used. Same technique to be used throughout the study
- Abdominal ultrasound for liver (only at screening)
- Bone imaging dual-energy x-ray absorptiometry [DXA] scan - total hip, lumbar spine (read locally) (DXA to be performed during Screening, only if not performed within 20 weeks prior to signing ICF)
- 6MWT (6-minute walk test) at Week -4 and between Week -3 and Week -2

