- SF-36 v2 – The SF-36 version 2 is a 36-item generic PRO questionnaire used to assess patient-reported HR-QoL outcomes. The SF-36 yields scores for eight domains of health: Physical Functioning (PF), Role-Physical (RP), Bodily Pain (BP), General Health (GH), Vitality (VT), Social Functioning (SF), Role Emotional (RE), and Mental Health (MH) as well as physical component summary (PCS) and mental component summary (MCS) scores. The SF-36 is scored such that higher scores reflect a better health state. For this study, a 7-day recall period is used.

Subjects will be asked to complete this quality of life questionnaire at Screening and every other dose (at Dose 1 Day 1, Dose 3 Day 1, Dose 5 Day 1 and thereafter) in the DBTP and at 9 weeks after last dose, as detailed in [Table 3](#). The questionnaire must be always completed by the subjects before knowing the predose Hb test result. In the OLP, subjects will complete this quality of life questionnaire every other dose as detailed in [Table 3](#).

- FACIT-F – The FACIT-Fatigue, is a multidimensional, self-report quality of life instrument. It consists of 27 core items, the Functional Assessment of Cancer Therapy - General (FACT-G) questionnaire, which assesses patient function in 4 domains: Physical, Social/Family, Emotional, and Functional well-being, which is further supplemented by a 13-item measure designed to capture cancer-related fatigue, the Fatigue subscale (FS). The items are measured on a response scale with five options (0 = not at all to 4 = very much) and has a 7-day recall period.

Subjects will be asked to complete this quality of life questionnaire at Screening and every other dose (at Dose 1 Day 1, Dose 3 Day 1, Dose 5 Day 1, and thereafter) in the DBTP and at 9 weeks after last dose, as detailed in [Table 3](#). In the OLP, subjects will complete this quality of life questionnaire every other dose as detailed in [Table 3](#). The questionnaire must be always completed by the subjects before knowing the predose Hb test result.

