4.3. Stratification, Randomization, and Blinding

Subjects will be randomized to receive luspatercept or placebo at a 2:1 ratio. Randomization will be accomplished by an IRT to ensure timely registration and randomization. A stratified block randomization schedule will be implemented. Randomization will be stratified by:

- Baseline hemoglobin level
 - a. ≥ 8.5 g/dL
 - b. < 8.5 g/dL
- Baseline NTDT-PRO T/W score
 - a. ≥ 3 points
 - b. < 3 points

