4.4. Sample Size Determination

Based on the assumption of targeted primary endpoint response rates of at least 50% in the luspatercept group and 10% for the placebo group, and 2:1 randomization, a total sample size of

150 (100 in the luspatercept group, 50 in the placebo group) will have at least 99% power to detect the difference between the 2 groups with a 2-sided alpha of 0.05 and assumed 10% dropout rate.

For NTDT-PRO T/W domain scores, assume the mean change from baseline scores at Week 24 are 1.2 and 0.5 for luspatercept and placebo group, respectively, with a common standard deviation of 1.2, the statistical power will be 91%.

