5. GENERAL STATISTICAL CONSIDERATIONS

5.1. Reporting Conventions

Summary tables, listings, figures and any supportive SAS outputs will include a “footer” of explanatory notes that will indicate, at a minimum, the following:

- Program source (e.g., SAS program name, including the path, that generates the output) and
- Data extraction date (e.g., the database lock date, run date)

The purpose of the data extraction date is to link the output to a final database, either active or archived, that is write-protected for replication and future reference. An output date will also appear on each output page and will indicate the date the output was generated by the analysis program.

The following reporting conventions apply generally to tables, listings, and figures:

- Data from all study centers will be combined for analysis;
- The randomization stratification variables used in the analyses will be derived based on the electronic case report form (eCRF) data.
- All statistical tests of the treatment effect will preserve a significance level of 0.050 for 2-sided tests. Testing of interactions will be performed at the 0.100 significance level, unless specified otherwise;
- P-values will be rounded to 4 decimal places. P-values that round to 0.0000 will be presented as ‘<0.0001’ and p-values that round to 1.000 will be presented as ‘>0.9999’;
- Confidence intervals (CIs) will be presented as 2-sided 95% CIs unless specified differently in specific analysis;
- Summary statistics will consist of the number and percentage of subjects in each treatment group for discrete variables, and the sample size, mean, median, Standard Deviation (SD), Q1, Q3, minimum, and maximum for continuous variables;
- All mean, median, Q1, and Q3 values will be formatted to one more decimal place than the measured value. Standard deviation values will be formatted to two more decimal places than the measured value; Minimum and maximum values will be presented to the same number of decimal places as the measured value.
- All percentages will be rounded to one decimal place. The number and percentage of responses will be presented in the form XX (XX.X%), where the percentage is in the parentheses; when the number of a response is zero, percentage will not be presented for that response;
- All listings will be sorted for presentation in order of treatment group, study center, subject, and date of procedure or event if not otherwise specified;

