- All listings will display original collected values, cases with special marks (i.e., <500) will be listed as it is. The special mark will be removed if the value is used for calculation in tables;
- All analysis and summary tables will have the analysis population sample size (ie, number of subjects) if not otherwise specified;
- All summary tables will be displayed by treatment (“Luspatercept” and “Placebo”), the “Total” group will be added for sections if specified;
- In general, if not otherwise specified, baseline value will be defined as the last value (including “unscheduled”) on or before the first dose of IP (if collecting time is available, date/time will be used to compare with first dosing date/time to identify baseline record, if there is no time available, only date will be used); if multiple values are present for the same date/time, the average of these values will be used as the baseline. For subjects who were not treated, the value on or prior to randomization date will be used. Specifically, for the laboratory hematology parameter ‘Leukocytes’, the baseline is defined as the highest value between screening visit and dose 1 day 1 visit.
- For data handling in change from baseline and shift tables (except for MRI and DXA parameters), “unscheduled” visits will be grouped with the closest scheduled visit based on assessment date. The average will be used as value for that scheduled visit in change from baseline tables; the worst category will be used in shift tables. If an unscheduled visit has equal distance to two scheduled visits, it will be grouped with the later visit. Specifically, for anti-drug antibody (ADA) titer summary, the titer value will not be averaged if an “unscheduled” visit is mapped to the closest scheduled visit. The titer for “unscheduled” visit will only be used for summary if the original scheduled visit has no titer result.
- For hemoglobin (Hb) concentration related efficacy endpoints summary, specific intervals are defined as:
 - Baseline 4-week interval: from Week -4 (Day -27 with an allowable administrative 3-day window) to Dose 1 Day 1 (Day 1). The details of the baseline definition will be specified in the programming specification.
 - Weeks 13 - 24 interval is chosen in the following order:
 - a. Average of all Hb measurements in Weeks 13-24 (Day 86 to Day 169) if Weeks 13-24 has ≥ 3 Hb measurements
 - b. Average of all Hb measurements in Weeks 12-23 (Day 79 to Day 162) if Weeks 12-23 has ≥ 3 Hb measurements

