10.4 Analyses of Other Secondary Efficacy Endpoints

The analyses of other secondary efficacy endpoints will be performed on the ITT population except for the FACIT-F and SF-36 endpoints listed in this section. The analyses of NTDT-PRO, FACIT-F, and SF-36 endpoints will be conducted based on the Health Related QoL evaluable population (Section 5.2.4).

10.4.1 FACIT-F Fatigue Subscale (FS): Mean Change from Baseline between Weeks 13 to 24 and Weeks 37 to 48

Mean FACIT-F FS score change from baseline over a 12-week interval between Weeks 13 to 24 (nominal Dose 5 to Dose 9) will be analyzed using ANCOVA method with treatment group, randomization stratification factor(s) in the model and baseline FACIT-F FS score as covariate. The baseline of FACIT-F FS is the score from the last visit prior to or on Dose 1 Day 1.

Mean change from baseline for Weeks 37 to 48 (nominal Dose 13 to Dose 17) will be analyzed similarly.

The subgroup analyses for Weeks 13-24 will be performed as described in Section 10.5.

10.4.2 NTDT-PRO SoB Score: Mean Change from Baseline between Weeks 13 to 24 and Weeks 37 to 48

Mean NTDT-PRO SoB score change from baseline over a 12-week interval between Weeks 13 to 24 will be analyzed using ANCOVA method with treatment group, randomization stratification factor(s) in the model and baseline NTDT-PRO SoB score as covariate. Similar analysis will be performed for Weeks 37 to 48.

10.4.3 Hemoglobin Mean Change Between Weeks 37 to 48

Mean Hemoglobin change from baseline over 12-week interval between Weeks 37 to 48 during the treatment period will be analyzed using ANCOVA method with treatment group and randomization stratification factor(s) in the model as covariates.

Baseline hemoglobin (Hb) is the average of 2 or more Hb measurements at least 1 week apart within 4 weeks prior to Dose 1 Day 1. The Hb values within 21 days following a transfusion may be influenced by the transfusion and will be excluded from this analysis. For discontinued subjects who do not complete 24 weeks of the DBTP, Hb data will continue to be collected. For a subject, if the Hb average over Weeks 37-48 interval cannot be calculated due to missing data, the closest Hb 12-week average will be used.

10.4.4 NTDI-PRO (T/W Domain) Mean Change Between Weeks 37 to 48

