For subjects who have one response and continue to respond at the efficacy cutoff date, the end day of the response will be censored at the date of efficacy cutoff and the duration of response will be calculated as date of efficacy cutoff – first day of response + 1, where date of efficacy cutoff is defined in Section 10. For subjects who have multiple responses and their last responses continue on the efficacy cutoff date, the longest response will be the last one if the duration from the response start to censoring is longer than all the previously occurred response durations. If the continuing response duration is not the longest compared with the previously occurring responses, the response with the longest duration will be selected. Summary statistics will be provided for the total duration of hemoglobin response within the entire study period and the ratio of the total response duration versus entire study duration. The entire study duration is defined as period from Day 2 to date of efficacy cutoff.

10.4.14 6MWT: Mean Change at Week 24 and 48

For 6MWT assessments, mean changes from baseline at Weeks 24 and 48 will be summarized descriptively and analyzed using ANCOVA method with treatment group, randomization stratification factor(s) and baseline 6MWT value as the covariates. In addition, subgroups of subjects with baseline 6MWT ≤ 450 meters and > 450 meters will be performed. Other subgroup analyses will be added as described in Section 10.5.

Mean changes from baseline at Week 48 will be analyzed similarly.

10.4.15 Proportion of Mean Hemoglobin Increase from Baseline ≥ 1.5 g/dL at Week 13 to 24

Similar to the primary efficacy analysis, the proportion of subjects who have an increase from baseline ≥ 1.5 g/dL in mean of hemoglobin values over a continuous 12-week interval from Week 13 to Week 24 in the absence of transfusions will be performed on the ITT population. The Hb values within 21 days following a transfusion may be influenced by the transfusion and will be excluded from this analysis. Cochran-Mantel-Haenszel (CMH) test will be performed with treatment group and randomization stratification factor(s) in the model to compare the treatment and placebo groups at 2-sided 0.05 level.

10.4.16 Proportion of subjects with a decrease from baseline \geq (RD) in mean NTDT-PRO T/W score, over Weeks 13 to 24 and Weeks 37 to 48

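### FACIT-F, SF-36 and 6MWT are adjusted for the last pre-dose value only; adding the earlier value already collected is an optional, near-free gain in precision

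*SAP*

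**What the plan says.** **Baseline rule.** SAP 5.1: "In general, if not otherwise specified, baseline value will be defined as the last value" on or before the first dose. Values are averaged only when they share a date and time. No other rule is given for SF-36 or 6MWT, so this default applies to them. FACIT-F has its own sentence in SAP 10.4.1, to the same effect: "The baseline of FACIT-F FS is the score from the last visit prior to or on Dose 1 Day 1".

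**What is collected.** For both SF-36 and FACIT-F, Protocol 6.8 says: "Subjects will be asked to complete this quality of life questionnaire at Screening and every other dose (at Dose 1 Day 1", and so on. Protocol Table 3 agrees, which gives two pre-dose scores. For the walk test, Protocol 6.1 lists "6MWT (6-minute walk test) at Week -4 and between Week -3 and Week -2", which gives two pre-dose walks. A third is possible. Protocol Table 2 and the dosing-visit cell of Table 3 both name Dose 1 as a walk-test visit, but the Dose 1 column of Table 3 is blank for it.

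**How baseline enters the models.** FACIT-F is analysed by ANCOVA with the baseline score as covariate (SAP 10.4.1). SF-36 uses a repeated-measures model with baseline and time-by-baseline terms (SAP 10.4.6). 6MWT uses ANCOVA with "randomization stratification factor(s) and baseline 6MWT value as the covariates" (SAP 10.4.14).

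**Contrast.** For hemoglobin, SAP 10.2 averages two or more pre-dose values.

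**The concern.** A pre-randomisation measurement of the outcome is usually among the best covariates available. Here a second one is collected for each of three measures and is not used. If a single score or walk varies from visit to visit around the subject's underlying level, the second value carries information that the first does not. Leaving it out makes the residual variance larger and the confidence intervals wider than the collected data require. Health-related quality of life and physical activity are stated secondary objectives, the sample is fixed at about 150, and SAP 4.4 states no power for these endpoints.

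**Working it through.** **Inputs from the documents**
- Test level: "All statistical tests of the treatment effect will preserve a significance level of 0.050 for 2-sided tests".
- Allocation: "Subjects will be randomized to receive luspatercept or placebo at a 2:1 ratio".
- Size: "150 (100 in the luspatercept group, 50 in the placebo group) will have at least 99% power to" detect the primary difference (SAP 4.4).
- FACIT-F outcome: SAP 10.4.1 maps Weeks 13-24 to nominal Doses 5 to 9. With every-other-dose completion this gives Doses 5, 7 and 9, which fall 12, 18 and 24 weeks after Dose 1.

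**Assumptions**
- Pre-dose questionnaires at Weeks -4 and 0; walks at Weeks -4 and -2.5; one follow-up walk at Week 24.
- All correlations are assumed. The documents give none.

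**1. The plan's own figure.** The only continuous endpoint with stated power is NTDT-PRO T/W (difference 0.7, SD 1.2, 91%). SE = 1.2 × √(1/50 + 1/100) = 0.208; 0.7/0.208 = 3.37; power = Φ(3.37 - 1.96) = 92.0%. The t distribution gives 91.7%, and 90 versus 45 after 10% dropout gives 89.2% (normal). The figure reproduces. It says nothing about FACIT-F, SF-36 or 6MWT.

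**2. Constant correlation.** With p pre-dose values, r averaged follow-up values and common correlation ρ, the residual variance as a fraction of the total is

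V = [1 + (r-1)ρ]/r - pρ²/[1 + (p-1)ρ].

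FACIT-F at ρ = 0.5, r = 3: p = 1 gives 2/3 - 0.25 = 0.417; p = 2 gives 2/3 - 0.5/1.5 = 0.333, a cut of 20.0%.

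| ρ | FACIT-F, 1 → 2 values | Cut | 6MWT, 1 → 2 values | Cut |
|---|---|---|---|---|
| 0.5 | 0.417 → 0.333 | 20.0% | 0.750 → 0.667 | 11.1% |
| 0.6 | 0.373 → 0.283 | 24.1% | 0.640 → 0.550 | 14.1% |
| 0.7 | 0.310 → 0.224 | 27.9% | 0.510 → 0.424 | 17.0% |
| 0.8 | 0.227 → 0.156 | 31.4% | 0.360 → 0.289 | 19.8% |
| 0.9 | 0.123 → 0.081 | 34.6% | 0.190 → 0.147 | 22.4% |

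The ranges quoted in this point use 0.5-0.8 for FACIT-F and 0.5-0.9 for the walk.

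**3. Decaying correlation.** Let the correlation between two times be R × (1-d)^(weeks apart), where R is reliability and d the weekly loss. Example, 6MWT with R = 0.8 and d = 0.01:
- Week -4 with Week 24: 0.8 × 0.99^28 = 0.604.
- Week -2.5 with Week 24: 0.8 × 0.99^26.5 = 0.613.
- Between the two walks: 0.8 × 0.99^1.5 = 0.788.
- Last value only: 1 - 0.613² = 0.624.
- Both: 1 - (0.604² + 0.613² - 2 × 0.788 × 0.604 × 0.613)/(1 - 0.788²) = 0.586, a cut of 6.2%.

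The same calculation across R = 0.7, 0.8, 0.9:

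| Weekly loss | FACIT-F cut | 6MWT cut |
|---|---|---|
| 1% | 12.3, 10.6, 6.4% | 6.7, 6.2, 4.1% |
| 2% | 6.4, 4.9, 2.4% | 3.2, 2.7, 1.5% |
| 3% | 3.6, 2.6, 1.1% | 1.6, 1.3, 0.7% |

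With no measurement error (R = 1) and decay, the gain from two covariates is nil, and a plain average of the two values is 2-3% worse than the last value alone.

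**4. SF-36.** For a single visit with constant correlation 0.5-0.8, the cut is 11-20%, as for one walk. With decay and a 24-week correlation of 0.5-0.7, it is 2.5-9.5% at R = 0.8 and 0.8-3.5% at R = 0.9. The full repeated-measures model was not worked through.

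**5. Covariates already in the model.** Each model includes the baseline T/W stratum. Suppose this binary factor correlates 0.4 with FACIT-F at every visit (assumed). The partial correlation at ρ = 0.5 is then (0.5 - 0.16)/(1 - 0.16) = 0.405. The formula in step 2 gives 0.439 → 0.370, a cut of 15.8% instead of 20.0%. The figures in steps 2 to 4 are therefore on the high side.

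**6. Interval width.** Width scales with √(1 - cut). A 1% cut narrows the interval by 0.5%, 12% by 6.2%, 20% by 10.6% and 31.4% by 17.2%.

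**The case against.** A last-pre-dose baseline is prespecified, conventional and unbiased. The documents do not contradict themselves on it, and no stated precision target is missed. All of this stands, and it is why the point is an optional improvement and not an error.

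The gain rests on assumed correlations. The 20-31% end requires a score taken four weeks before dosing to predict Week 24 as well as the Dose 1 score does. This also stands. A reader might turn the range into a typical power gain, such as 80% rising to 84-88%. The documents support neither the 80% start nor any correlation. From an assumed 80%, Φ(2.80/√(1 - cut) - 1.96) runs from 80.4% at a 1% cut to 92% at a 31% cut, and nothing singles out the middle.

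A reader might also infer that the plan contradicts itself because NTDT-PRO uses seven diary days at baseline. That comparison is not like for like. NTDT-PRO has 24-hour recall, whereas FACIT-F and SF-36 each have 7-day recall (Protocol 6.8), so one completion already covers a week. Only hemoglobin is a fair precedent.

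SAP 10.4.6 and Section 14 refer to a separate HRQoL SAP that was not available here. It might use the Screening scores for FACIT-F or SF-36. Nothing suggests that it covers 6MWT. The claim is therefore limited to the models in this SAP.

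Finally, the first walk may partly be practice. A constant shift between walks is absorbed when both values are covariates, but not when they are averaged for some subjects and not for others.

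**Conclusion.** The point holds as a modest matter of efficiency. The earlier pre-dose FACIT-F, SF-36 and 6MWT results enter no model specified in this SAP. Using them would reduce residual variance by about 1-12% (FACIT-F) or 1-7% (6MWT) if correlation decays by 1-3% a week at reliability 0.7-0.9. The reduction would be about 20-31% (FACIT-F 12-week mean) or 11-22% (6MWT at one visit) if correlation is constant over time. It could be near zero if measurement error is small and scores drift. These figures ignore the stratum covariates, which lower them somewhat.

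A reader might infer that the planned analyses are biased or invalid. They are not: both values precede treatment, and adjusting for one is valid. The primary and key secondary endpoints are untouched. The facts and the direction are firm, the size is not, and the priority is optional.

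**What to change.** Before unblinding, amend SAP 10.4.1, 10.4.6 and 10.4.14:
- Keep change measured from the last pre-dose value. The ≥ 3-point FACIT-F responder definition and the 37, 43 and 450 m cut-offs then stay as they are.
- Add the earlier pre-dose value (Screening FACIT-F FS, Screening SF-36 score, earlier 6MWT) as a second baseline covariate. For SF-36, also add a time-by-earlier-value term. Two covariates are safer than an average, which can lose precision when scores drift.
- If the earlier value is missing, fill it by a rule blind to treatment, for example the subject's other pre-dose value or the pooled mean. Without such a rule, the complete-case approach in SAP 10.6 would drop that subject.
- State whether a Dose 1 6MWT is done and counts, and reconcile Protocol Tables 2 and 3. If it is done, it becomes the last value and there are two earlier walks to use.
- Align the separate HRQoL SAP.

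The cost is a few sentences and one or two degrees of freedom per model. No new data are needed, and the gatekeeping sequence is unaffected.

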Grade 3 leukocytosis ^f	Discontinue treatment ^d

AE: adverse event; Hb: hemoglobin; WBC: white blood cell.

^a Possibly, probably, or definitely related.

^b If dose delay is > 15 consecutive weeks, treatment should be discontinued.

^c Based on the predose Hb value not influenced by transfusion (ie, > 21 days post-transfusion); Hb should be rechecked weekly during dose delay.

^d Additional treatment discontinuation criteria are in Section 11.1.

^e Central lab corrected WBC values should be used in DBPT and OLP for confirming the Investigator's decision, which may be based on local results. Baseline = highest WBC value between Screening WBC and Dose 1 Day 1.

^f Grade 3 leukocytosis (WBC > 100,000/mm³) should be confirmed by central lab values.

^g Per CTCAE: Grade 1 leukopenia: < LLN – 3000/mm³; Grade 1 neutropenia: < LLN – 1500/mm³; Grade 1 thrombocytopenia :< LLN – 75,000/mm³; Grade 2 Leukopenia: <3000 – 2000 / mm³; Grade 2 Neutropenia: < 1500 – 1000 / mm³; Grade 2 Thrombocytopenia :< 75,000 – 50,000 / mm³.

^h Per CTCAE: Grade 3 leukopenia: < 2000 - 1000/mm³, neutropenia: < 1000 - 500/mm³ and thrombocytopenia: < 50,000 – 25,000/mm³.

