11.4.1 Hematology/Chemistry/Immunology

The laboratory results and change from baseline will be summarized by visit by treatment group for central lab hematology and chemistry panels separately.

A shift table representing the shift from the baseline grade to maximum NCI-CTC Grades (high or low) will be provided for selected hematology and chemistry parameters having toxicity grade by visit by treatment group. The shift summary for high category will be done for hepatic function parameter (ALT, AST, ALP, total bilirubin) and renal function parameter (serum creatinine and eGFR by MDRD). The shift summary for low category will be done for hematology parameter (platelets, leukocytes and absolute neutrophil counts).

To estimate the incidence of subjects who have passed the predefined threshold for selected parameters, a summary table representing the number and percentage of subjects with lab assessments satisfying the threshold criteria will be provided by treatment group. A subject with post-baseline result (including “unscheduled” visits) meeting the criteria will be counted. The threshold criteria include below:

LIVER FUNCTION

Post-baseline Alanine Aminotransferase (ALT)	$\geq 3x$ upper limit of normal (ULN)
Post-baseline Aspartate Aminotransferase (AST)	$\geq 3x$ ULN
Post-baseline Total Bilirubin (BILTOTAL)	$\geq 2x$ ULN
Post-baseline ALT/AST and BILTOTAL	(ALT $\geq 3x$ ULN or AST $\geq 3x$ ULN) and BILTOTAL $\geq 2x$ ULN
RENAL FUNCTION	
Post-baseline eGFR by MDRD (CREATCLR)	$< 0.5x$ baseline
Post-baseline Serum Creatinine (CREAT)	$> 2x$ baseline
Albuminuria Category (ACR: mg/g)	<30
	$\geq 30 - \leq 300$
	$>300 - \leq 1000$
	$>1000 - \leq 3500$
	>3500
HEMATOLOGY	
Post-baseline Leukocytes (WBC)	$\geq 2x$ baseline and $> ULN$
	$\geq 3x$ baseline and $> ULN$
	$\geq 2x$ baseline and $> ULN$ and lasts for at least 42 days
	$\geq 3x$ baseline and $> ULN$ and lasts for at least 42 days
Maximum Post-baseline Platelets (PLAT)	$\geq 1.5x$ baseline and $> ULN$
	$\geq 600 - < 1000 \times 10^9/L$
	$\geq 1000 \times 10^9/L$

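### The highest-value WBC baseline, defined in the protocol for the 2x/3x rise rules, is applied to every leukocyte table, so within-arm mean change is biased downward and low-grade shifts are probably over-counted

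*SAP*

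**What the plan says.** SAP Section 5.1 introduces its rules with "The following reporting conventions apply generally to tables, listings, and figures". The default is that "baseline value will be defined as the last value" on or before first dose. Leukocytes are the named exception: "the baseline is defined as the highest value between screening visit and dose 1 day 1 visit". The exception is not limited to particular outputs, and no second leukocyte baseline is defined.

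SAP Section 11.4.1 then uses a leukocyte baseline in three kinds of output:

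- By-visit change: "The laboratory results and change from baseline will be summarized by visit by treatment group for central lab hematology and chemistry panels separately".
- The CTCAE shift table: "The shift summary for low category will be done for hematology parameter (platelets, leukocytes and absolute neutrophil counts").
- The threshold table, which counts WBC at or above 2x and 3x baseline.

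The exception has a source in the protocol. Footnote e to Table 5 (Section 7.2.1.2) reads "Baseline = highest WBC value between Screening WBC and Dose 1 Day 1". In that table the footnote mark is attached only to the 2x and 3x WBC rise rows. The leukopenia rows carry footnotes g and h, which give CTCAE grade limits and no highest-value rule.

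**The concern.** The highest of several fluctuating pre-dose values sits above the subject's usual level. That makes a fold-rise threshold harder to reach, and the protocol chose it for that purpose. In a mean-change table it has a different effect: a subject whose WBC has not moved shows a fall. For a low-direction shift it selects the mildest pre-dose grade, so an ordinary fluctuation at follow-up is more likely to count as worsening. Platelets and neutrophils in the same shift table keep the last-value baseline, so the three cell lines are not measured from comparable starting points.

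WBC is a safety parameter of interest in both directions. What is at stake is how the within-arm change columns and low-grade shift counts in the safety report are read.

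**Working it through.** The plan states no figure on this point, so there is none to reproduce.

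**Direction.** For every subject, the highest pre-dose value is at least as large as the last. So change = follow-up - baseline is equal or lower, and the baseline low grade is equal or milder. This needs no distributional assumption. Follow-up does not offset it: SAP Section 5.1 averages grouped values in change tables and takes the worst category in shift tables.

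**Number of values.** Protocol Table 3 schedules hematology twice in screening and again at Dose 1 Day 1. The SAP refers to a single screening visit. The maximum is therefore over two or three values.

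**Built-in fall with no drug effect.** For independent normal errors, E[max of 2] = 0.564 SD and E[max of 3] = 0.846 SD. If the pre-dose errors have a correlation of 0.5 (assumed), multiply by √(1 - 0.5) = 0.707, which gives 0.40 and 0.60 SD.

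The documents give no within-subject WBC variability, so a CV of 10% to 30% is assumed. For log-normal values with s² = ln(1 + CV²), E[max of 2]/mean = 2Φ(s/√2).

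- CV 10%: s = 0.0998 and 2Φ(0.0705) = 1.056, a change of -5.6%.
- CV 30%: s = 0.2936 and 2Φ(0.2076) = 1.164, a change of -16.4%.
- Three values, evaluated numerically: -8.6% to about -26%.
- Last value: 0.

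**Effect on a true 10% rise, two values.** As a percentage of the true pre-dose mean, 110 - 105.6 = +4.4% at CV 10%, and 110 - 116.4 = -6.4% at CV 30%.

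**Between-arm difference.** Both arms are randomized and use the same baseline rule, so the same expected excess is subtracted from each and cancels. In a simulation with median WBC 6 x10⁹/L, CV 20% and a true 10% rise in one arm, the difference in mean change is +0.66 x10⁹/L with either the last value or the highest of three.

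**Low-category shift, no drug effect.** The grade cut-offs of 3, 2 and 1 x10⁹/L come from Table 5 footnotes g and h. Assumptions: LLN 4, log-scale between-subject SD 0.3, within-subject CV 15%.

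| Typical WBC (x10⁹/L) | Follow-up | Last value | Highest of 2 | Highest of 3 |
|---|---|---|---|---|
| 5.5 | single visit | 8.0% | 10.8% | about 12.3% |
| 8 | single visit | 1.2% | 1.5% | about 1.6% |
| 5.5 | worst of 16 visits | 33.9% | 39.5% | about 41.2% |

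A wider between-subject spread (CV 40%) at a typical WBC of 8 gives 2.4% rising to 3.1% or 3.5% for a single visit. The worst-of-16 row is shown because Section 11.4.1 describes a shift to the maximum grade but also says it is presented by visit. On the worst-grade reading the relative excess is smaller: 39.5/33.9 = 1.17 and 41.2/33.9 = 1.22 at 5.5, and about 10% to 26% across the WBC levels tried at CV 15%.

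**The case against.** The choice is deliberate and prespecified. It keeps one WBC baseline across protocol and SAP, and having two has a cost: the same subject would start from different values in adjacent tables. These are descriptive tables with no test or decision rule attached. For leukopenia the error is toward over-counting, in both arms. All of this stands and limits the weight of the point. It does not explain why a rule written for fold-rises should govern mean change and low-direction shifts.

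Three stronger readings are tempting, and the documents do not support them.

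- A reader might infer that a real rise in WBC could be hidden in the trial. The placebo column carries the same built-in fall, observed values are tabulated beside the changes, and the 2x/3x counts are also planned. The distortion is in the within-arm change column.
- A reader might infer that the WBC plot over time is distorted. SAP Section 11.4.1 plots test values, not changes from baseline, so it is unaffected.
- A reader might infer that dose holds or malignancy and marrow work-ups are affected. Those are per-subject actions at dosing visits under Table 5 and do not depend on these summary tables.

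The link to the shift table is also an inference. Section 11.4.1 does not define baseline grade; the general convention in Section 5.1 implies it.

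**Conclusion.** The point holds as a matter of within-arm reporting. The direction is certain for the leukocyte change-from-baseline table. It holds for the low-category shift table if baseline grade follows Section 5.1.

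The sizes are illustrative. The built-in fall is about 6% to 16% with two pre-dose values or 9% to 26% with three, for an assumed CV of 10% to 30% and independent values; correlation reduces it. With two values, a true within-arm rise of 10% would show as about +4% to -6%. At CV 15% the excess in single-visit low-grade worsening runs from a few tenths of a percentage point at a typical WBC of 8 to about 3 to 4 points at 5.5, where LLN and between-subject spread are also assumed. The absence of between-arm bias is shown for mean change only; the shift counts are raised in both arms.

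This is a cheap improvement. It does not threaten the trial's conclusions.

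**What to change.** In SAP Section 5.1, limit the highest-value leukocyte baseline to the 2x/3x WBC threshold outputs that mirror Protocol Table 5. State that the leukocyte change-from-baseline and low-category shift tables use the general last-value baseline, as platelets and neutrophils already do. In Section 11.4.1, say which baseline the shift table's baseline grade is taken from. The WBC time plot needs no change, and the protocol's dosing rule is untouched.

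The cost is one sentence, one extra derived baseline flag, and a table footnote explaining that a subject can have two WBC baselines. No new data are needed.
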